Main study parameters/endpoints: The primary outcome variable is changes in mood variability. The secondary outcome variables are changes in levels of depression, mania, anxiety, general level of functioning and level of hopelessness, number of relapses into mania and depression and changes in imagery characteristics.

Nature and extent of the burden and risks associated with participation, benefit and group relatedness: Risks for patients participating in this study are minimal. ImCT intervention has been successfully tested in a pilot study (Holmes et al., 2016) and an audit (Hales et al., 2018), suggesting this intervention is able to decline mood variability in patients suffering from bipolar disorder, and is also well tolerated and well received by patients. The

psychoeducation intervention closely resembles care as usual but is during this study delivered more structured by using a protocol. All patients, during the baseline period, during both treatments and during the follow-up period have regular appointments with their psychiatrist, who prescribes, monitors and adjusts mood stabilising medication. Should patients relapse into mania or depression, they will receive standard care as usual. Both interventions, ImCT and psychoeducation treatment are carried out conform existing protocols. The extra burden for patients, is the weekly questionnaires (20 minutes), and the questionnaires at T0-T4 (45 minutes), as daily mood monitoring is advised in current guidelines and part of care as usual.

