6.2 Randomisation, blinding and treatment allocation

An independent central research assistant will randomize participants to treatment condition (ImCT or psychoeducation) after checking all in- and exclusion criteria. Randomization will be based on block randomization with (N=10) per block to guarantee a balance between conditions over time and stratified for mood stabilising medication (either mood stabilising medication, or no mood stabilising medication), so that mood stabilising medication is controlled per arm. Stratification for mood stabilising medication is necessary because not using mood stabilizing medication can seriously affect the primary outcome variable. We roughly estimate that 15 percent of the participants in GGzE will have no mood stabilising medication, but there are no firm data available. Blinding of participants and therapists to treatment condition is not possible in this kind of psychotherapy trial, but the assessments will be blind to treatment condition as they are filled in online.

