8. STATISTICAL ANALYSIS

First, descriptive analyses will be used to establish mean scores, standard deviations and to identify outliers. Missing data from our primary outcome variable, will be listwise deleted. In our other outcome variables, data will only be included if pre- and post-measures are completed.

Second, the data will be checked with respect to violation of assumptions (such as error independency, non-normal distributions) for variance-based models.

Primary outcome variable: mood variability:

To assess if there is a stronger decrease in mood variability in the ImCT intervention condition as compared to the psychoeducation condition, multivariate repeated measures analyses are applied. Dependent variables are the scores on the ALS-18 (baseline, T0; pre-treatment, T1; post-treatment, T2; 8-weeks follow-up, T3; 16-weeks follow-up, T4) with treatment condition (ImCT, psychoeducation) as between subjects variable.

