In addition, to assess reductions in mood variability during the interventions (ImCT, psychoeducation) compared to mood variability during the baseline period, daily mood measures with the National Institute of Mental Health Life Chart Methodology (NIMH-LCM) Prospective Self-Rating of mood (both mania and depression) are assessed, using a case series design, where participants baseline ratings can act as their own control (Arntz, Sofi, & van Breukelen, 2013). Changes in mood variability are investigated using sequence analysis with R-software (package TraMineR version 1.8-10); (Gabadinho, Ritschard, Muller, & Studer, 2011) on the daily scores. Sequences consist of a series of subsequent states (daily scores) and similarities between sequences are calculated with the Optimal Matching technique (OM). Sequences will be defined as day scores from 28 days prior to starting the interventions, until 112 days after the end of interventions. Rather homogenous groups of trajectories (clusters) will be derived from the distance matrix that result from the OM technique. To this end, cluster analysis will be applied. Shannon entropy of transversal state of the scores on each day will be calculated and plotted (Gabadinho et al., 2011). Entropy is a measure of diversity of states (a measure of mood variability) within sequences and varies between zero (all sequences in the same state) to 1 (maximum diversity). To explore the relationship between diversity in states (mood variability) and background characteristics, this longitudinal entropy will be regressed on co-variates (gender, medication). Also, sequences of scores at the start of treatment will be compared to subsequences during treatment and during the follow-up period to explore change over time.

Secondary outcome variables: depression, anxiety, mania, general functioning and coping, hopelessness, number of relapses into mania or depression, and changes in imagery:

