Where possible multivariate analyses are used to analyse differences between groups, and repeated-measures ANOVA to analyse difference within groups. These will be used to minimise the correlations and dependencies between variables. In order to allow for reliable multivariate analysis, assumptions of sphericity are tested. Multivariate analyses between groups (ImCT, psychoeducation treatment) and repeated-measures ANOVA within groups (T0, T1, T2, T3, T4) are used to determine an omnibus effect. If differences are significant, post hoc analyses (mostly independent T-test) will be used to determine individual differences between groups and between points in time. Bonferoni corrections are used to correct for multiple testing.

Intention-to-treat analyses will constitute the central analyses and completers analyses will be done as supplementary analyses.

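### The mood-stabiliser stratum used in randomisation is left out of the ALS-18 and secondary-scale models; adding stratum and stratum-by-time would recover any lost precision at almost no cost.

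*Combined protocol and SAP*

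**What the plan says.** Section 6.2 makes mood-stabiliser use, yes or no, the stratification factor and explains why: "Stratification for mood stabilising medication is necessary because not using mood stabilizing medication can seriously affect the primary outcome variable". It sizes the smaller stratum only loosely: "We roughly estimate that 15 percent of the participants in GGzE will have no mood stabilising medication, but there are no firm data available". Allocation is blocked: "Randomization will be based on block randomization with (N=10) per block".

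Section 8 specifies the primary analysis as repeated measures of the ALS-18 at T0 to T4, "with treatment condition (ImCT, psychoeducation) as between subjects variable". No other between-subjects term is named. The continuous secondary scales (symptoms, functioning, hopelessness, imagery) are analysed in the same way. After a significant omnibus result, "post hoc analyses (mostly independent T-test) will be used to determine individual differences between groups and between points in time". Medication appears as a covariate only in the exploratory analysis of the daily life-chart scores, where "this longitudinal entropy will be regressed on co-variates (gender, medication)". That regression is not the between-arm comparison of the ALS-18.

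The Summary words the endpoint as change: "The primary outcome variable is changes in mood variability".

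**The concern.** The protocol declares a factor important enough to stratify on and then does not use it in the analysis that the stratification is meant to serve. Stratified allocation makes the arms similar on medication, so the true sampling variance of the arm difference contains little of the between-stratum spread. A model without the stratum still counts that spread as residual error. Where the stratum is prognostic for the quantity being compared, the reported standard error is therefore larger than it should be, the test rejects less often than 5% under the null, and power is lower than the same data could give.

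The design has little slack: the planned 45 per arm gives only just over 80% power. Leaving adjustment unstated also leaves that choice open until after the data are seen.

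**Working it through.** **The plan's own figure.** Section 4.4 uses d = 0.6, two-sided 5%, 80% power and a two-sample t-test. The noncentral-t calculation gives 44.6, so 45 per arm, with power 80.4%. This reproduces the stated 45. The dropout of 1 in 15 gives 45 × (1 + 1/15) = 48, as stated; dividing instead, 45 / (1 − 1/15) = 48.2, gives 49. The difference does not matter here.

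**Inputs.** Unmedicated proportion p = 0.15 (Section 6.2), or about 0.15 × 96 = 14 patients. Blocks of 10 (Section 6.2). The medicated-unmedicated difference in ALS-18, d_s, in within-stratum SDs, is not in the documents and is assumed over a range. The simulations also assume a within-person correlation of 0.6.

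**Single-visit comparison.** With exact balance, the unadjusted standard error exceeds the stratum-adjusted one by the factor √(1 + p(1 − p)d_s²), where p(1 − p) = 0.15 × 0.85 = 0.1275.

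- d_s = 0.5: √(1 + 0.1275 × 0.25) = √1.0319 = 1.016
- d_s = 0.8: √(1 + 0.1275 × 0.64) = √1.0816 = 1.040
- d_s = 1.0: √(1 + 0.1275) = √1.1275 = 1.062

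At d_s = 1.0 the excess is 4.4% if 10% are unmedicated (√1.09) and 9.0% if 25% are (√1.1875).

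A simulation with N = 90, 15% unmedicated and permuted blocks of 10 within stratum (20,000 null runs, 8,000 power runs, true effect 0.6 within-stratum SD) gave:

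| d_s | Unadjusted SE / true SD of estimate | Type I error, unadjusted | Type I error, adjusted | Power, unadjusted | Power, adjusted |
|---|---|---|---|---|---|
| 0.5 | 1.01 | 4.8% | 5.1% | 79.7% | 80.5% |
| 0.8 | 1.04 | 4.2% | 5.0% | 77.2% | 79.6% |
| 1.0 | 1.05 | 3.8% | 4.7% | 77.1% | 80.7% |

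A separate simulation of 40,000 trials with exact balance (41:41 and 7:7) gave type I error of 4.55% at 0.5 SD and 3.84% at 1.0 SD. The group main effect follows the same formula if d_s is expressed in SDs of each person's mean over visits.

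**Group-by-time comparison (post minus pre).** If unmedicated patients score d_s higher at every visit, the shift enters both measurements and cancels: d_s − d_s = 0. In the same simulation, constant shifts of up to 1.5 SD gave standard-error ratios of 0.99-1.00, type I error of about 5%, and power of 88-89% with or without adjustment.

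If the stratum also alters the change itself:

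| Assumed stratum effect on change | Unadjusted SE / true SD of estimate | Type I error, unadjusted | Power, unadjusted | Power, adjusted |
|---|---|---|---|---|
| 0.5 SD | 1.02 | 4.6% | 87.7% | 88.6% |
| 0.8 SD | 1.04 | 4.1% | 86.3% | 88.5% |

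**Sample size after the change.** Keeping d = 0.6 on the total SD and 45 per arm, power moves from 80.4% to 80.8%, 81.6%, 83.3% or 84.8% for d_s = 0.3, 0.5, 0.8 or 1.0. The number per arm needed for 80% power is 45, 44, 42 or 40. The planned size does not need to rise.

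**The case against.** A reader might infer that every standard error in the ALS-18 model is too wide. The documents do not support that. The hypothesis in Section 2 and the question put in Section 8 are about a larger fall in one arm than in the other, which is the group-by-time effect, and a constant medication shift drops out of it. Section 6.2 says that non-use can affect the outcome but does not say whether it means level or change. The Summary's wording of the endpoint as change makes an effect on change a fair reading, but no figure backs it. This objection stands and limits the point.

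A reader might also infer that the stratification is wasted. It is not: its stated purpose is to control medication per arm, and protection against chance imbalance remains without adjustment. Only a possible gain in precision is given up.

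The effect is also small. At 0.5 SD the single-visit power loss is under one percentage point, and nothing in the documents supports a difference as large as 1.0 SD. The post hoc t-tests run only after a significant omnibus test. Section 5.2 lets medication be adjusted throughout, so status at randomisation may predict later visits less well. These are reasons to rate the point as modest. They do not argue for leaving the stratum out, because the simulated power is essentially unchanged by adjustment when the stratum has no effect.

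Two features of the plan add some weight to including it. About 14 unmedicated patients in blocks of 10 will probably end on an incomplete block, and the listwise deletion in Section 8 can disturb balance further.

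**Conclusion.** The omission is certain; its effect is conditional and small. For single-visit arm comparisons and the group main effect, standard errors are conservative to the extent that medication predicts ALS-18 level. At one visit with 15% unmedicated, the excess is about 1.6% at an assumed 0.5 SD and about 6% at 1.0 SD, with type I error of about 4.6-4.8% and 3.8%. For the group-by-time test, the standard error is right under a constant shift and about 2-4% too wide if medication alters change by an assumed 0.5-0.8 SD.

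These sizes rest on assumed stratum effects, on the protocol's own rough 15%, and, for the change results, on an assumed correlation of 0.6. The error is in the safe direction, so it should not be read as bias or as a source of false positives. The case for acting is that the plan's own premise calls for the term and including it is nearly free.

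**What to change.** In Section 8, include the randomisation stratum (mood stabiliser yes/no, as recorded at randomisation) and stratum-by-time in the ALS-18 repeated-measures model and in the models for the continuous secondary scales. Take between-arm contrasts at each visit from the stratum-adjusted model instead of from unadjusted independent t-tests. Stratum-by-time must be named: a stratum main effect alone is constant within a person and, with complete data, leaves the group-by-time error unchanged. The chi-square test of relapses does not take an added fixed factor, so this change does not extend to it.

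The cost is one sentence, one between-subjects degree of freedom and four for stratum-by-time over the five ALS-18 visits (for the weekly scales, the number of weekly occasions less one). The variable is already needed for randomisation, and the sample size stays as planned.

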6. METHODS

6.1 Study parameters/endpoints

6.1.1 Main study parameter/endpoint

To assess the primary endpoint of this study (1), decrease of mood variability, mood variability is measured using the Affect Lability Score Short Version (ALS-18) (Oliver & Simons, 2004) at baseline (T0), pre- intervention (T1) and post intervention (T2), and at follow-up measurements at 8 (T3) and 16 weeks (T4) after treatment discontinuation in both the ImCT and psychoeducation conditions. The ALS-18 is a self-report scale measuring lability in affect and consists of 18 items. Ratings are made on a 4-point scale with a maximum score of 72. Scores range from A= very characteristic of me (4 points), to D= very uncharacteristic of me (1 point).

In addition we monitor changes in mood variability using the National Institute of Mental Health Life Chart Methodology (NIMH-LCM) Prospective Self-Rating (Denicoff et al., 2000). Participants rate their mood (both mania and depression) on a 9-point Likert scale, ranging from -4 (severe depression, admission required due to severe dysfunction) to 0 (stable mood) to +4 (severe mania, admission required due to severe dysfunction). Daily measurements are calculated during a 4-week baseline prior to start of either ImCT or psychoeducation, during the intervention and until follow up at 16 weeks. This method is advised given that traditional self-report mood ratings over a single time point are scarcely representative of mood variability in bipolar disorder.

6.1.2 Secondary study parameters/endpoints (if applicable):

The following parameters are used for the following secondary objectives:

To assess (2a) level of depression, mania and anxiety and (2b) general functioning and hopelessness (3) number of relapses into mania or depression decline/increase, we administer the following measures:

- Level of depression, using the Quick Inventory of Depressive Symptoms (QIDS-SR) (Rush et al., 2003). The QIDS-SR is a 16-item self-report rating scale in which the nine DSM 5 symptoms of major depression are incorporated. Answers are rated on a four-point Likert scale (0-3). The QIDS-SR is administered weekly throughout the duration of the study.

- Level of mania, using the Altman Self-Rating Mania Scale (ASRM-NL) (Altman, Hedekker, & Peterson, 1997). The ASRM-NL is a 5 item self-report instrument to measure severity of mania symptoms. This is administered weekly throughout the duration of the study.

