- Level of anxiety, using the Beck Anxiety Inventory (BAI) (Osman, Barrios, Aukes, Osman, & Markway, 1993). The BAI is a 21-item self-report questionnaire used for measuring the severity of anxiety. Answers are rated on a 4-point Likert scale (0-3). This is administered weekly throughout the duration of the study.
- Level of general functioning and coping: Participants rate their level of functioning using the Longitudinal Interval Follow up Evaluation – Range of Impaired Functioning Tool (Leon et al., 1999). This is a brief scale for people suffering from affective disorders, measuring four different functional areas (employment, interpersonal relations, satisfaction and recreation) on a 5-point Likert scale (low rating implies higher functioning). This is administered at T0, T1, T2, T3 and T4.
- Level of hopelessness: participants rate their hopelessness using the Beck Hopelessness Scale (Beck, Brown, & Steer, 1997), The BHS is a 20 item self-report scale measuring three aspects of hopelessness: feelings about the future, motivation and expectations. The BHS demonstrates good internal consistency (alpha = .93) and has high reliability in psychiatric samples (Beck et al., 1997). The BHS is administered at T0, T1, T2, T3 and T4.
- To assess number of relapses into mania and depression, scores on the above measures (ASRM for mania and QIDS-SR for depression) are used. Scores on the ASRM of 5 or more indicate a relapse into mania, a score of 10 or more on the QIDS a relapse into depression. This is measured using the weekly scores on the ASRM and QIDS-SR during the weekly measures in the follow up period (until 16 weeks after the end of either ImCT or psychoeducation).

To assess if (4) problematic imagery the following measures will be used:

- The Visual Analogue Scales of Imagery Characteristics (VAS-Imagery) have been tailored to BD populations. The scales range from 0-9. Examples are "How real / vivid / absorbing / preoccupying / compelling have your image(s) been over the past week"; "To which extent could you understand the role that the image(s) play in your mood instability?"; "To which extent could you find positive / helpful way of using the image(s)?" Target imagery is measured weekly throughout the duration of the study. Imagery characteristics are measured weekly throughout the duration of the study in both ImCT and psychoeducation treatment conditions.

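### Section 6.2 calls the assessments blind because they are completed online, but after randomisation every listed outcome is rated by participants who know their treatment

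*Combined protocol and SAP*

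**What the plan says.** Section 6.2 makes two statements in one sentence. The first is "Blinding of participants and therapists to treatment condition is not possible in this kind of psychotherapy trial". The second is that "the assessments will be blind to treatment condition as they are filled in online". Online completion is the only reason given for the second.

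Section 6.1.1 describes the primary measure: "The ALS-18 is a self-report scale measuring lability in affect and consists of 18 items". For the daily NIMH-LCM it says "Participants rate their mood (both mania and depression) on a 9-point Likert scale". Section 6.1.2 adds further scales completed by the participant, among them "The QIDS-SR is a 16-item self-report rating scale" and "The BAI is a 21-item self-report questionnaire used for measuring the severity of anxiety".

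Section 6.3.2 has participants fill in T2, T3 and T4, and the daily and weekly measures, during and after the allocated treatment. Section 6.3.3 allows paper completion as an alternative, and withholds assessment results from patients and therapists until the end of the study.

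**The concern.** An assessment is blind when the person making the rating does not know the allocation. If the rater is the participant, and the participant knows the treatment, putting the form online changes nothing in that respect. The plan would then claim a protection that it does not have.

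What is at stake is how the result may be described. A primary result reported as blind-assessed invites the reader to discount expectancy and reporting bias. A result described as unblinded self-report does not. The trial is also meant to inform a larger RCT (Section 4.4 gives N = 350), so the description may be carried forward with the estimate.

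**Working it through.** **Step 1: who rates each outcome (Sections 6.1.1 and 6.1.2).**

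| Outcome | Rater |
|---|---|
| ALS-18 (primary) | participant, self-report |
| NIMH-LCM, daily mood | participant, self-rating |
| QIDS-SR, depression | participant, self-report |
| ASRM-NL, mania | participant: "The ASRM-NL is a 5 item self-report instrument to measure severity of mania symptoms" |
| BAI, anxiety | participant, self-report |
| LIFE-RIFT, functioning | participant: "Participants rate their level of functioning using the Longitudinal Interval Follow up Evaluation" |
| BHS, hopelessness | participant, self-report |
| Relapse | cut-offs on ASRM (5 or more) and QIDS-SR (10 or more), both self-rated |
| VAS-Imagery, MICQ-BD, DImS | participant; items and surveys on the participant's own imagery |

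The documents describe no independent assessor, clinician-rated outcome or blinded adjudication of relapse.

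**Step 2: does the stated reason support the claim?** Online forms remove influence from an interviewer. They do not conceal treatment from someone who has attended it. Withholding results (Section 6.3.3) stops patients and therapists from seeing scores; it does not stop the patient from knowing the arm. The number-coding of data in Section 10.1 protects identity and is not a statement about the rater.

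**Step 3: which ratings are affected?** T0 and the four weeks of daily and weekly baseline ratings precede allocation, so they are made without knowledge of treatment. T2, T3, T4 and all ratings during treatment and follow-up are made with that knowledge. T1 is unresolved: Section 6.3.2 has participants complete T1 and then be allocated, while Section 9.2 has them allocated and then complete T1.

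**Step 4: size.** The documents give no figure for reporting bias, so no figure follows from the contradiction itself. For scale, start from the plan's own calculation in Section 4.4 (d = 0.6, two-sided 5%, 80% power, 45 per group). For a two-sample t-test with n per group, the noncentrality is d × √(n/2) on 2n − 2 degrees of freedom. With n = 45 this is 0.6 × √22.5 = 2.85 on 88 degrees of freedom, and the power is 0.804. The 45 reproduces.

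Now assume no true effect, and a reporting shift b, in SD units, between the arms:

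| Assumed b | Noncentrality b × √22.5 | Chance of p < 0.05 | b / 0.6 |
|---|---|---|---|
| 0 | 0 | 5.0% | 0% |
| 0.1 | 0.47 | 7.6% | 17% |
| 0.2 | 0.95 | 15.5% | 33% |
| 0.3 | 1.42 | 29.1% | 50% |

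These rates describe unblinded self-report under an assumed shift. They do not measure the effect of the faulty clause, and correcting the clause does not change them. They also belong to a simple t-test, whereas Section 8 plans a multivariate repeated-measures analysis over T0 to T4, with Bonferroni-corrected post hoc tests after a significant omnibus result.

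**The case against.** The strongest defence is that nothing is hidden. The sentence that makes the claim also says that participants are unblinded, and Section 6.1.1 labels the ALS-18 as self-report. The intended meaning may be only that no staff member who knows the allocation scores the outcome. No input to the sample size and no analysis step depends on the claim. This stands as far as intent goes: a reader might infer that the sponsor is concealing a weakness, and the documents do not support that. It does not rescue the wording, because being blind to treatment condition is a stronger property than having no interviewer.

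Other stronger readings also fail:

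- **That the bias must favour ImCT.** The plan presents ImCT as new and promising and psychoeducation as near to usual care, which makes this plausible. But the comparator is an active, protocolised treatment with the same 12 contact hours (Section 3), and each arm may receive the other treatment after the study (Section 11.1). The direction is not documented.
- **That the false-positive rate is inflated by a known amount.** The rates in the working rest on an assumed shift and a test that is not the planned one.
- **That every rating is unblinded.** T0 and the baseline-period ratings are not.
- **That self-report is itself a design error.** In a psychotherapy trial where blinding is not possible, it is an acceptable choice. The error is the label.

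**Conclusion.** Wrong as written. The plan attributes blindness to assessments whose rater, after randomisation, is always an unblinded participant. This follows from the text alone and needs no numerical assumption. It affects the primary ALS-18, the daily mood ratings and all listed secondary outcomes, including relapse, because the comparison between arms rests on post-randomisation ratings.

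Its practical weight lies in what may be claimed about the result, not in sample size or analysis. The size and direction of any bias are unknown. The range of about 8% to 29% is an illustration for assumed shifts of 0.1 to 0.3 SD at 45 per arm and should not be cited as the trial's error rate. Whether T1 is also rated with knowledge of treatment cannot be settled until the two accounts of its timing are reconciled.

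**What to change.** 1. In Section 6.2, replace the closing clause with: *All outcomes are self-reported; ratings after randomisation are made by participants who know their treatment, so outcome assessment is not blind. Online completion only avoids influence from an interviewer.*
2. In Section 8 or the reporting plan, state that differences between the arms on these measures may include expectancy or reporting bias and may not be reported as blind-assessed.
3. Reconcile Sections 6.3.2 and 9.2 on the order of T1 and allocation, and say which ratings are made before allocation is known.
4. Optional: mask the arm labels for the ALS-18 analysis, indexed T0 to T4, until its code is locked. This does nothing about self-report bias. It is not feasible for the daily and weekly series, whose length reveals the arm: 4 + 12 + 16 = 32 weeks for ImCT against 4 + 6 + 16 = 26 weeks for psychoeducation (Section 3).

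Items 1 to 3 cost a few sentences and need no change to outcomes, visits or sample size. The downside is a less favourable description of the design. Item 4 adds a small amount of data handling.
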